8 EARLY PARTICIPANT WITHDRAWAL OR DISCONTINUATION

Participants may discontinue the study due to consent withdrawal or withdrawal due to an AE. The Investigator may elect at any time to discontinue a participant for any reason if such a decision is in the participant's best medical interest or it is determined the participant is not

compliant with the protocol. If a participant discontinues the study for any reason, or is withdrawn by the Investigator, the primary reason for termination or discontinuation should be documented on the CRF.

9 EARLY STUDY END

If the study is ended prematurely or suspended:

- The Sponsor or representative will promptly inform the Investigators of the termination or suspension and the reasons and inform the regulatory authority(ies) (where required by applicable regulatory requirements)
- The IRBs will be promptly informed and provided with the reasons(s) for termination or suspension by the Sponsor or by the Investigator

If the Investigator (or IRB) terminates or suspends the investigation without prior agreement of the Sponsor:

- The Investigator will promptly inform the Sponsor and the IRB, provide a detailed written explanation of the termination or suspension, and, if feasible, designate another qualified Investigator to be trained and continue follow-up of already-enrolled participants. The new Investigator/site would be requalified by the Sponsor or representative. Participants would be re-consented.
- The Investigator will inform the institution (where required by applicable regulatory requirements)
- The Investigator will promptly inform the participants and ensure appropriate therapy and follow-up for the participants
- The Sponsor or representative will inform the regulatory authority(ies) (where required by applicable regulatory requirements)

10 ADVERSE EVENTS

The Investigator is responsible for the detection and documentation of events meeting the definition of an AE or SAE as provided in this protocol. Only treatment emergent AEs and SAEs, occurring after randomization through the end of the study visits will be recorded. All AEs, including SAEs that occur during the participant's study participation, must be documented in the participant's source document and CRF.

10.1 Definition of an Adverse Event

An adverse event is any untoward medical occurrence, associated with the use of an investigational product, whether or not considered related to the investigational product. An AE is any unfavorable and unintended sign, symptom or disease temporally associated with the use of an investigational product and does not imply any judgement about causality. AEs will be considered study-related if the event follows a reasonable temporal sequence from a study-

related procedure or device and could readily have been produced by the study procedure or device.

An event that emerges during treatment having been absent pre-treatment or worsens relative to the pre-treatment state should be reported as a TEAE.

Laboratory or functional test abnormalities generally are not considered AEs unless they are associated with clinical signs or symptoms or require medical intervention.

An AE includes:

- Exacerbation of a pre-existing illness
- Increase in frequency or intensity of a pre-existing episodic event or condition
- Condition detected or diagnosed after investigational product placement even if present prior to the start of the study
- Continuous persistent disease or symptoms present at Baseline that worsen following the start of the study

Adverse events occurring to any study participant during study participation will be reported by the site to the study Sponsor or representative by means of the AE CRF. The AE CRF includes severity, seriousness, action taken, causality and outcome of each event. The Medical Monitor will determine if the AE meets the threshold for a Major Adverse Event (MAE), will verify UADE status, and will determine the relatedness of the event to the device and/or procedure.

All adverse events will be coded and summarized by tabulating the number and percentage of participants reporting each event (AE, SAE, and UADE) for the safety population. An AE that is related to the device is called an Adverse Device Effect (ADE).

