2.3 Risk and Benefit Assessment

2.3.1 Potential Risks

The only known study-related risk is the use of a nasal cannula to deliver cold air to the participant. The potential risks associated with this delivery are:

Nosebleed

Shivering

Irritation of the nasal passages

Skin irritation at the site of the cannula

Nasal congestion

Over cooling

Participants will be de-identified using a study specific number at the time of enrollment. All Case Report Forms (CRFs) will be labeled with the de-identified participant identification (ID) number. No identifiable participant identification information will be provided to NeuroIntact.

Information collected for this study is confidential. However, officials of the Food and Drug Administration (FDA) or other regulatory agencies may research records during the ordinary course of carrying out their functions. A Sponsor representative may also inspect the research records to make certain the study data is accurate. The Investigator, regulatory agencies, and the Sponsor will protect the confidentiality of the records.

2.3.2 *Risk Mitigation*

The protocol has been designed to minimize the risks to study participants enrolled in the study. In general:

- Prior to study enrollment the Investigator must ensure the participant meets the inclusion/exclusion criteria
- Each participant will be fully informed about the conditions of study participation, and the risks and potential benefits of the study procedure and asked to provide an executed Informed Consent prior to being enrolled in the study
- Institutional Review Board (IRB) review and approval of the study protocol, Informed Consent Form, and any other participant-facing documents will be obtained prior to study initiation.
- The participant's core temperature will be continuously monitored with direction to adjust the VCool if the core temperature is $<35^{\circ}\text{C}$ for a sustained period of 5 minutes, to mitigate overcooling of the participant
- If the participant develops a nosebleed, the VCool will be stopped
- Participants will be assessed for shivering and if severe according to the Bedside Shivering Assessment Scale, the VCool flow and temperature will be adjusted

2.3.3 *Potential Benefits*

The information obtained in this study will not benefit the study participants directly but may aid future patients requiring cooling of body temperature.

2.4 *Study Rationale*

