5.3 Safety Considerations

All treatment emergent adverse events (TEAEs) reported by participants will be tabulated.

Each adverse event (AE) will be evaluated by the Investigator in terms of seriousness, severity (mild, moderate, severe) and relationship (not related, possibly related, probably related, definitely related) to the study device.

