10.5 Assessment of Relatedness to Study Product

The Investigator or designee will assess each AE and SAE for causality based on their best medical judgement, the observed symptoms associated with the event, and the available information on the investigational product.

- Not Related: No evidence of any causal relationship with the investigational device or trial intervention.
- Possibly Related: Some evidence to suggest a causal relationship between the AE and the investigational device or trial intervention, but other factors may have contributed to the event.
- Probably Related: Evidence suggests a causal relationship with the investigational device or trial intervention; the influence of other factors is unlikely.
- Definitely Related: Evidence suggests a causal relationship to the investigational device or trial intervention, i.e., follows a known or suspected pattern of response, or is otherwise logically related to the investigational device or trial intervention, and no alternative cause is present.

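### Sections 5.3, 10.1 and 10.5 rate adverse events against different things and by two roles, so an MRI-caused event could be classed as device-related or not; separately, the stated risks leave out MRI.

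*Protocol*

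**What the plan says.** **Who rates.** Section 5.3, matching the Synopsis, gives the task to the Investigator: "Each adverse event (AE) will be evaluated by the Investigator in terms of seriousness, severity (mild, moderate, severe") and relationship. Section 10.5 agrees but allows a delegate: "The Investigator or designee will assess each AE and SAE for causality based on their best medical judgement". In Section 10.1 the site enters causality on the adverse event CRF, and the Medical Monitor then "will determine the relatedness of the event to the device and/or procedure".

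**Against what.** Section 5.3 asks for "relationship (not related, possibly related, probably related, definitely related) to the study device". Section 10.5, the only place that defines the four levels, words all of them on a combined target; the lowest reads "No evidence of any causal relationship with the investigational device or trial intervention". Section 10.1 covers device, procedure or both, and counts an event as study-related if it follows from a study-"related procedure or device and could readily have been produced by the study procedure or device". The ADE definition in Section 10.1 and the SADE definition in Section 10.2 refer to the device only.

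**Stated risk.** Section 2.3.1 says: "The only known study-related risk is the use of a nasal cannula to deliver cold air to the participant". Neither its list nor the anticipated events in Section 11 mentions MRI. Yet Sections 4.1 and 7.6.2 put every participant through baseline and repeated MRI, and Section 6.2 excludes anyone with a contraindication to it.

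**What is tabulated.** Section 10.1 names adverse events, serious adverse events and UADEs. Section 12.2 adds the incidence and nature of adverse events. Neither names an ADE or SADE row.

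**The concern.** Safety of the device is part of the study objective (Section 2.2), and Section 2.1 presents this as the first study to lower core temperature with thermoelectrically cooled nasal air. Attribution to VCool is therefore information that readers will want from it.

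Cooling and imaging happen in the same session, so timing alone will often not separate their effects. If the CRF is built from Section 10.5, it holds one rating for device and trial intervention together, and no later analysis rule can split that rating. The scope problem is thus one of data capture, and a statistical analysis plan could not repair it afterwards. The choice of reported rating, by contrast, could be settled in such a plan, but the protocol now gives the decision to two roles.

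**Working it through.** The protocol gives no figure on this point to reproduce, so the check is a comparison of texts.

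**Step 1: rater and scope by section**

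| Protocol section | Rater | Related to what |
|---|---|---|
| Synopsis, 5.3 | Investigator | Study device |
| 10.1, review sentence | Medical Monitor | Device, procedure or both |
| 10.5 | Investigator or designee | Device or trial intervention, one merged scale |
| 10.1 (ADE), 10.2 (SADE) | Not stated | Device |

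The ADE and SADE definitions need a device-only rating. Section 5.3 would supply one, but the level definitions in Section 10.5 do not match it. For example, the second level reads "Some evidence to suggest a causal relationship between the AE and the investigational device or trial intervention".

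**Step 2: follow one event judged to be caused by MRI and not by VCool**

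- Section 5.3: not related, because MRI is not the study device.
- Section 10.1, review sentence: related, through the procedure.
- Section 10.5: related if trial intervention includes MRI; not related if it means cooling only. The section does not say which.
- ADE or SADE: should be no. If the Section 10.5 rating is the only one recorded and is read broadly, the event cannot be told apart from a device effect.

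**Step 3: which outputs move**

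- Adverse event and serious adverse event counts: no change, since neither depends on relatedness.
- Prompt reporting of serious events: no change. Sections 11.3 and 16 apply whether or not the device is implicated.
- ADE and SADE: they change with the section followed.
- UADE: possibly. Section 11.2 requires a serious effect tied to use of VCool and not identified in the protocol. No MRI event is identified in Sections 2.3.1 or 11, so a serious MRI event rated as related on the merged scale could be carried into this class. The Medical Monitor's check of UADE status may prevent that.

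**Step 4: size, by illustration**

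Assume a denominator of n = 10, from the 10 completers in Section 7.3.1. One reclassified participant moves the proportion by 1/10 = 10 percentage points. Exact (Clopper-Pearson) 95% limits for assumed counts:

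- 0/10: upper limit 1 − 0.025^(1/10) = 30.8%, so 0 to 30.8%
- 1/10: 0.3 to 44.5%
- 2/10: 2.5 to 55.6%

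These limits hold for any yes/no result in 10 people and say nothing about how often reclassification would occur. Section 10.1 uses a safety population, and screening continues until 10 participants complete. Treated participants who stop early could take the denominator above 10 and make each shift smaller.

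**Step 5: risk statement**

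Section 2.3.1 admits only one known study-related risk. Section 6.2 treats MRI as unsuitable for some people, and Sections 4.1 and 7.6.2 make it a main study procedure. These statements do not fit together. This is a fault in the risk text and does not by itself alter any count.

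**Step 6: Major Adverse Event**

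Section 10.1 asks the Medical Monitor to judge events against a threshold for this class. The protocol text gives neither a threshold nor a definition.

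**The case against.** The strongest reply is that no planned table is affected. A reader might infer that the safety result as a whole is indeterminate. The documents do not support that: the tabulation named in Section 10.1 has no ADE or SADE row, and all-event and serious-event counts stand whatever the rating. This part of the reply stands.

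Second, the two roles can be read in sequence, with the site rating first and the Medical Monitor deciding after. That is a fair reading of Section 10.1. The rating used in tables, and the level that counts as related, are often left to a statistical analysis plan, which is not at hand. Their absence is therefore not the fault here. What remains is that Sections 5.3 and 10.5 give the Investigator a decision that Section 10.1 gives to someone else.

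Third, trial intervention may mean cooling alone, since Section 10.5 is headed as relatedness to the study product. On that reading Sections 5.3 and 10.5 agree and only Section 10.1 is wider, where separate determinations are possible. This is plausible, but the text does not settle it.

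Fourth, a reader might infer from Section 2.3.1 that participants are told of only one source of risk. That cannot be concluded: the consent form is not at hand, and Section 2.3.2 promises full information about risks. The point is limited to the protocol's own sentence.

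**Conclusion.** The protocol is inconsistent on attribution. It uses three wordings for the scope of relatedness and two roles for the decision, while the ADE and SADE definitions rest on the device alone. An MRI-caused event could therefore be classed as device-related or not, depending on the section followed. The effect is confined to ADE, SADE and possibly UADE classification. The 10-point shift per participant assumes a denominator of 10 and that at least one event is open to both readings; the protocol offers no basis for estimating how likely that is. The conclusion also assumes that the CRF follows Section 10.5 and that trial intervention can be read to include MRI.

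The sole-risk sentence in Section 2.3.1 conflicts with Sections 4.1, 6.2 and 7.6.2 under any reading of the relatedness scale. For a 10-person descriptive study these are modest faults, but they are best corrected before data collection.

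**What to change.** - Record two causality ratings for each adverse event on the existing four-point scale: one for VCool, one for MRI or other study procedures.
- Use the VCool rating for ADE, SADE and UADE classification.
- Align the Synopsis and Sections 5.3, 10.1 and 10.5 to these two ratings. State whether the Investigator's or the Medical Monitor's rating is final, and list any disagreement. Either choice works if it is named.
- Amend the risk sentence in Section 2.3.1 to include MRI.
- Define the Major Adverse Event threshold in Section 10.1, or remove the reference.

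The cost is one extra CRF field and minor wording changes. The sample size, procedures and planned all-event tables stay as they are.

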10.2 Definition of a Serious Adverse Event

A serious adverse event (SAE) or serious adverse device effect (SADE) is any AE that resulted in any of the following outcomes:

- Death
- Life-threatening -the participant was, in the opinion of the Investigator, at immediate risk of death from the AE as it occurred
- Disability or incapacity
- Inpatient hospitalization* or prolongation of existing hospitalization
- Important medical events that may not result in death, be life-threatening, or require hospitalization may be considered an SAE when, based upon appropriate medical judgement, they may jeopardize the participant and may require medical or surgical intervention to prevent one of the outcomes listed in this definition
- Fetal distress, fetal death, or congenital abnormality

*Planned hospitalization for an existing condition is not an SAE. Hospitalization is defined as greater than 24 hours in the hospital.

An SAE that is related to the device is called a serious adverse device effect (SADE).

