10.6 Reporting Serious Adverse Events

Prompt notification of the Sponsor regarding SAEs is essential so that regulatory responsibilities and legal obligations can be satisfied. The Investigator must report SAEs according to the following time frames.

- Initial notification of all SAEs based on the available information must be provided to the Sponsor or designee by phone within 24 hours of the investigational site learning of the event. Initial notification within 24 hours of death or life-threatening events is extremely important.
- Follow-up information, when available, must be sent to the Sponsor or designee within 48 hours of receipt of the information by the investigational site

The Investigator must comply with all applicable local regulatory requirements related to reporting SAEs to the IRB.

The Investigator should institute appropriate therapeutic and follow-up measures in accordance with good medical practice and should notify the monitor of such actions and record them in the participant's CRF.

10.6.1 *Serious Adverse Event Information to Report*

At a minimum, SAE reports must contain the participant ID number, the serious adverse event term, onset date, relationship to study product, and a brief description of the event. Causality should be included in the initial report.

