11.3 Reporting

All AEs, UADEs, and SAEs will be reported via the CRFs. All AEs meeting the above definitions of an UADE and/or SAE, whether device-related or not, must also be reported to the study Sponsor within 24 hours of discovery and to the approving IRB as soon as possible, based on IRB requirements but in no event later than 10 working days after the Investigator first learns of the AE or effect.

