13.1 Data Quality Assurance

Standardized paper CRFs will be used at the investigational site. The PI is responsible for ensuring completion and timely submission of the forms to the study Sponsor or designee for data processing. All data are reviewed to identify inconsistent or missing data and AEs. All

hard copy forms will be secured to ensure confidentiality. The PI is required to maintain all source documents as required by the protocol, including any applicable supporting medical records and Informed Consents. The source documents may be reviewed to verify information submitted on the CRFs.

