16 INVESTIGATOR REPORTS

The PI will be responsible for the following reports:

- AEs: SAEs, SADEs, and UADEs shall be reported to the Sponsor by fax or email within 24 hours of the Investigator becoming aware of the event
- All other AEs will be reported to the Sponsor via the Adverse Event CRF.
- AEs must also be reported to the reviewing IRB in compliance with its reporting requirements. For serious adverse events (whether or not device-related), this is typically no later than 10 business days of the Investigator becoming aware of the event.
- An Investigator shall submit to the reviewing IRB a report of any UADE occurring during an investigation as soon as possible, but in no event later than 10 working days after the Investigator first learns of the effect
- Protocol Deviations: The Investigator is responsible for reporting all protocol deviations to the Sponsor and to the IRB in compliance with the IRB's reporting requirements. The Sponsor will provide a deviation log and CRF to document protocol deviations.
- Withdrawal of IRB Approval: The Investigator shall report to the Sponsor within 5 working days if, for any reason, the IRB withdraws approval to conduct the investigation. The report will include a complete description of the reason(s) for which approval was withdrawn.

Other Reports: Upon request of the Sponsor, the FDA, or the IRB, the Investigator shall provide accurate, complete, and current information.

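### Section 14 stops following unresolved adverse events at 24 hours while Section 6.3 asks for no follow-up; a lesser point is that Section 10.2 leaves admissions of 24 hours or less to judgement for SAE reporting.

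*Protocol*

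**What the plan says.** **Follow-up.** Section 14 provides 24 hours of follow-up for adverse events that have not resolved, and does not say when the 24 hours begin. Section 6.3 describes one visit of about 4 hours and states that nothing further is required of the participant. Section 10.4 requires an outcome for every event. Its list includes not resolved, resolving and unknown beside the resolved and fatal categories.

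**Hospitalization.** Section 10.2 makes inpatient hospitalization a seriousness criterion and qualifies it in a footnote: "Hospitalization is defined as greater than 24 hours in the hospital". Planned admissions for an existing condition are excluded by a separate sentence. An important medical event that meets no other criterion "may be considered an SAE when, based upon appropriate medical judgement".

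**Reporting.** For SAEs, Section 10.6 says: "Initial notification of all SAEs based on the available information must be provided to the Sponsor or designee by phone within 24 hours". Section 11.3 applies the same limit to events that meet the SAE or UADE definition. These "must also be reported to the study Sponsor within 24 hours of discovery and to the approving IRB as soon as possible", and for the IRB "in no event later than 10 working days after the Investigator first learns of the AE or effect". For the rest, Section 16 says: "All other AEs will be reported to the Sponsor via the Adverse Event CRF". Section 13.1 sets no hour or day limit for that form: "The PI is responsible for ensuring completion and timely submission of the forms to the study Sponsor or designee for data processing". Section 16 keeps an IRB route for all events: "AEs must also be reported to the reviewing IRB in compliance with its reporting requirements".

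**The concern.** By Section 2.1, this is the first study to use thermoelectrically cooled air through a nasal cannula to lower core temperature. The participants are healthy and gain nothing directly (Section 2.3.3). Section 11 lists the expected nasal and skin effects and calls them transient. A rule that ends follow-up at 24 hours cannot confirm this for an event still open then. It also releases the site from staying in touch with a volunteer whose event has not settled. Section 6.3, read alone, could lead staff to omit even the 24 hours.

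The hospitalization footnote raises a smaller matter. A volunteer admitted overnight for an adverse event would not meet the hospitalization criterion, so whether the sponsor hears within 24 hours would depend on how the investigator or the Medical Monitor classifies the event.

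**Working it through.** The protocol states no figure to reproduce here. The check sets its rules side by side.

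**Follow-up**

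1. Section 14: follow-up of unresolved events lasts 24 hours, start not stated. Section 6.3: none required. The two agree only if Section 14 is read as an exception that Section 6.3 does not mention.
2. Effect of the unstated start. Section 10 records events only up to the end of the visit, and the visit lasts about 4 hours. If the clock starts at onset, and onset is at the earliest the start of the visit, follow-up ends 24 − 4 = 20 hours after the visit. If it starts at the end of the visit, it ends 24 hours after. The range is about 20 to 24 hours, so the cap matters and the start hardly does.
3. Does another section extend the cap?
   - Section 10.6 asks for follow-up in line with good medical practice, but it sits under SAE reporting and gives no duration.
   - Section 7.6.3 assesses adverse events during the study and afterwards continues only core temperature monitoring until baseline is regained.
   - Section 13 requires continuing safety assessments, without a period after the visit.
   - None of these obliges the site to follow a non-serious event beyond 24 hours.
4. Data consequence. An event open at 24 hours receives one of three valid codes: not resolved, resolving or unknown. The field is filled, but the eventual course is not observed.

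**Hospitalization**

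| Case | Meets the hospitalization criterion | Sponsor limit | IRB limit |
|---|---|---|---|
| Unplanned stay over 24 hours | Yes, once 24 hours have passed | 24 hours | 10 working days |
| Stay of 24 hours or less, classed as SAE or UADE by judgement | No | 24 hours | 10 working days |
| Stay of 24 hours or less, not so classed | No | AE CRF, no hour or day limit | The IRB's own requirements |

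The second row has two routes. One is the important-medical-event clause of Section 10.2. The other is Section 11.2, whose UADE definition also takes in other unanticipated serious problems associated with the device and does not refer to the footnote. Both need someone to judge the event serious. The life-threatening and disability criteria also remain where they apply.

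**The case against.** **On follow-up.** One might say that Section 6.3 is a general remark about visits and Section 14 the specific rule, so staff can follow Section 14 as it stands. That is a fair reading, and it makes the conflict mild. It does not lift the 24-hour cap.

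A reader might go further and infer that Section 10.4 is breached, or that outcomes will be missing from the safety data. The documents do not support this: Section 10.4 accepts unresolved and unknown outcomes and nowhere demands resolution. A reader might also infer that the unstated start leaves the window open-ended. It shifts the end by about 4 hours at most, and since Section 14 concerns contacting participants, the end of the visit is the natural start.

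**On hospitalization.** The strongest reply is that the footnote is an explicit, workable threshold that contradicts nothing else in the protocol. Calling it wrong would need an outside definition of seriousness, which this review does not rely on. This stands, and it is why the point is minor.

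The tempting stronger reading is that short admissions escape expedited reporting altogether or go unrecorded. They do not. Two judgement-based routes to the 24-hour notice remain. Even without them, the event goes on the AE CRF, the Medical Monitor decides on UADE status and relatedness (Section 10.1), and the IRB is told under its own rules. What is lost is only the automatic trigger.

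**Conclusion.** The main claim holds. As written, the protocol lets the site stop following an open adverse event roughly 20 to 24 hours after the visit, and Section 6.3 does not acknowledge even that much follow-up. The consequence is an unobserved course for any event that lasts longer, mainly non-serious nasal or skin effects, in a first use of this cooling method in healthy people.

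The minor claim holds as a remark on a chosen threshold. An unplanned admission of 24 hours or less becomes an SAE, or gets the 24-hour notice as a UADE, only by judgement.

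Both conclusions rest on the literal wording and on a visit of about 4 hours. The protocol gives no basis for the frequency of either case. With 10 planned completers, few events of either kind would be expected to decide anything. No efficacy endpoint is affected, and the two points are independent although both involve 24 hours.

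**What to change.** **Main change.** In Section 14, replace the 24-hour sentence with: *Adverse events unresolved at the end of the visit will be followed from that point until resolved or stable.* In Section 6.3, write: *No follow-up is required except for unresolved adverse events (Section 14).* This sets the start, removes the cap and settles the conflict. The cost is two sentences in an amendment and a few extra contacts with participants whose events are still open.

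**Optional change.** If the Section 10.2 footnote is revised, replace the duration sentence rather than only deleting it. It is the protocol's only definition of hospitalization, and without it a long emergency or observation stay with no formal admission would be open to argument. For example: *Any unplanned inpatient admission for an adverse event, or any stay of more than 24 hours in the hospital, counts as hospitalization.* Keep the sentence that excludes planned admissions for an existing condition. The cost is an occasional short admission reported as an SAE.
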